## **OBJECTIVES**

The objective is to establish evidence of Acceptance and Commitment Therapy (ACT) in combination with exercise in:

Primary Outcomes

- 1) Reducing pain intensity and interference;
- 2) Reducing depression;

Secondary Outcomes

- 3) Reducing anxiety;
- 4) Increasing psychological flexibility;
- 5) Increasing pain-related self-efficacy;
- 6) Increasing quality of life;
- 7) Increasing physical functioning

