## **METHODS**

### Design

This study adopts a cluster randomized trial design comparing older adults with chronic pain receiving ACT and exercise intervention to two arms: 1) art and exercise; and 2) treatment as usual (control group). 15-20 elderly from 10 different mental health service centres will be randomized to the experimental, sham, or active control group.

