### Participants

The effect size from previous literature and pilot data (0.25), an alpha=0.05, and power=0.8 was used to derive the total sample size of 135 participants. Assuming 10% attrition, total sample size = 150. Older adults with chronic pain (n=150) recruited from collaborating NGOs will be randomized into 3 different arms: 1) ACT and exercise; 2) art and exercise; and 3) treatment as usual.

Inclusion criteria are:

- age 60 years or above; and
- have depressive symptoms of mild level or above (PHQ > 5)
- have chronic pain (>3 months)
- able to give informed consent to participate

Exclusion Criteria:

- known history of autism, intellectual disability, schizophrenia-spectrum disorder, bipolar disorder, Parkinson's disease, or dementia
- (temporary exclusion criteria) imminent suicidal risk difficulty in communication
- have had stroke, fracture, cardiovascular disease, cardiovascular surgery, artery disease, surgery on vertebrae, and knee replacement in the past 6 months
- physical activity prohibited by a medical professional

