### *Primary Outcomes*

1. Feeling and Function in existence of pain: Brief Pain Inventory (BPI) (Cleeland, 1994) aims to evaluate the individual's pain experience and its effect on physical function on daily activities. The tool consists of 11 items, using an 11-point rating, of which 0 indicates not interference and 10 as interferes completely. The Cronbach's alpha coefficients for interference and severity subscales were .88 and 0.80 respectively (Cleeland, 1991). A validation on the Taiwanese population of BPI (BPI-T) was done by Ger et al in 1999.
2. Depression: The Patient Health Questionnaire (PHQ-9) (Kroenke, Spitzer, & Williams, 2001): a 9-item instrument that incorporates depression diagnostic criteria with other leading major depressive symptoms, and rates the frequency of the symptoms which factors into the scoring severity index. PHQ-9 scores of 5-9,

10-14, 15-19, 20 and above represent mild, moderate, moderately severe, and severe depression. The Cronbach's alpha coefficients for Primary Care Study and Ob-Gyn Study were .89 and 0.86 respectively. A validation on the Chinese version of PHQ- 9 was done by Yeung, Y. in 2010.

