## **Data Analysis**

Data will be analysed using a pre-post analysis based on different time points. For the main outcome measures of depressive symptoms/risks, wellbeing, and personal recovery, mixed ANOVA will be used to assess changes from T0/Intake to T1/exit between the two groups. To test for sustained effect after completion of intervention, mixed ANOVA will be used to assess depressive symptoms/risks, wellbeing, pain acceptance, physical ability, and symptoms of pain from T1/Exit to T2/FU within- and between- subjects. All results will be reported with the appropriate effect sizes, along with statistical significance and confidence intervals.

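### The sample size uses one undivided alpha of 0.05 and one power of 0.8 with no outcome or contrast named, although the protocol fixes two primary outcomes and two comparators

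*Protocol*

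**What the plan says.** - **Outcomes.** Objectives lists two primary aims: "Reducing pain intensity and interference", and reducing depression. Under Primary Outcomes the first is measured with the BPI, which has two subscales: "The Cronbach's alpha coefficients for interference and severity subscales were .88 and 0.80 respectively". Neither a total nor a lead BPI score is named. Depression is the PHQ-9.
- **Comparators.** Design compares older adults "receiving ACT and exercise intervention to two arms: 1) art and exercise; and 2) treatment as usual (control group"). Participants repeats that they "will be randomized into 3 different arms: 1) ACT and exercise; 2) art and exercise; and 3) treatment as usual".
- **Sizing.** Participants gives one calculation. It starts from "The effect size from previous literature and pilot data (0.25"), then "an alpha=0.05, and power=0.8 was used to derive the total sample size of 135 participants", and "Assuming 10% attrition, total sample size = 150". The metric of the 0.25, the outcome and the contrast are not stated.
- **Analysis.** Data Analysis plans a mixed ANOVA per outcome from intake to exit. It refers to two groups although there are three arms, and it names no pairwise test. It ends with "All results will be reported with the appropriate effect sizes, along with statistical significance and confidence intervals".

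**The concern.** A single alpha and power describe a single decision. With two primary outcomes, the decision could be that either suffices, that both are needed, or that they are tested in a fixed order, and the protocol does not say which. The figures in Participants fit only the last of these, and then only for the outcome placed first. Objectives numbers the outcomes but does not call the numbering a testing order.

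What is at stake is how a mixed result would be read. The stated objective is to establish evidence for ACT with exercise. One isolated significant result, for example on the PHQ-9, could be offered as that evidence with a false-positive chance above the stated 5%. If an alpha split or a both-must-succeed rule is adopted later, the trial will have less than the stated power for its claim.

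**Working it through.** **Inputs from the protocol.** Effect size 0.25, alpha 0.05, power 0.8, N = 135 before and 150 after 10% attrition (Participants); three arms (Participants); two comparators (Design); two primary outcomes (Objectives), or three scores if the BPI subscales are separate (Primary Outcomes).

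**Assumptions.** Equal arms (45 evaluable each), correlation between scores 0 to 0.8, independent observations (clustering ignored), two-sided pairwise tests.

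**1. The plan's own figures.** 135 / (1 - 0.10) = 150, which reproduces. A one-way three-group ANOVA with Cohen's f = 0.25 needs 158 (159 with equal arms), and 135 gives 73% power. The 135 is reached with an unstated assumption, such as ANCOVA with baseline correlation 0.4, or a repeated-measures between-group test with two measurements correlated 0.7. Read as a standardised difference d, 0.25 would need 252 per arm. So 135 is not shown to be wrong, but it is the size for one test at the full 0.05.

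**2. False-positive rate if any primary success counts, all null hypotheses true.** For k independent tests the rate is 1 - 0.95^k: k = 2 gives 9.8% and k = 3 gives 14.3%. For correlated scores, 400,000 sets of three arm means were simulated. The omnibus test is chi-square on 2 df; the pairwise tests use |z| > 1.96 and share the ACT arm. Ranges run from correlation 0 to 0.8.

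| Tests, each at 0.05 | Two outcomes | Three scores |
|---|---|---|
| One three-arm omnibus test per outcome | 9.7% to 7.9% | 14.3% to 10.0% |
| Pairwise against each comparator, only after a significant omnibus test | 8.1% to 6.6% | 12.0% to 8.5% |
| Pairwise, unadjusted, any significant result | 17.3% to 13.9% | 24.8% to 17.3% |
| Pairwise, unadjusted, only results favouring ACT | 8.8% to 7.0% | 12.9% to 8.7% |

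Every entry exceeds 5%.

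**3. Power if alpha is split.** One-way omnibus noncentrality is N f² = 135 × 0.0625 = 8.44 on 2 and 132 df. Power is 73% at 0.05 and 63% at 0.025. For 80% power the one-way total rises from 159 to 189.

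**4. Power if both primaries are required.** If one arm differs equally from two arms with the same mean, f = d√2/3, so d = 0.25 × 3/√2 = 0.53. With d = 0.53 on each outcome and correlation 0.5, the large-sample omnibus power of about 74% each (73% by the exact F test) becomes about 61% for both. Even with a true 80% on each, independent outcomes would give 0.8 × 0.8 = 64%.

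**5. Pairwise power.** With d = 0.53 and 45 per arm, noncentrality is 0.53 × √(45/2) = 2.51. Power is about 70% at 0.05 and 59% at 0.025.

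**The case against.** The strongest reply is that multiplicity procedures and success rules commonly sit in the statistical analysis plan, which is not shown. That stands: the absence of such a rule from the protocol is not the point here. But the sample size is a protocol statement. A later plan can control the error rate; it cannot make the Participants figures describe a split alpha or a joint claim.

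A reader might infer that the trial's false-claim rate is 15-25%. The document does not support that. It plans a mixed ANOVA per outcome and names no pairwise tests, and the top of that range also needs three separately tested scores. Two-sided rates also count false results against ACT. An omnibus result cannot say which comparator is beaten, so pairwise tests are a natural next step, but whether they would go unadjusted is not stated.

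A reader might also take the closing sentence of Data Analysis to mean that each result is judged at 0.05. It only says that significance will be reported.

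It is also fair to object that the family of primary tests is uncertain. Data Analysis lists depressive symptoms, wellbeing and personal recovery as the main outcomes from intake to exit, with pain appearing only from exit to follow-up. This conflicts with Objectives and must be reconciled. The working follows Objectives and Primary Outcomes, where the primaries are named.

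**Conclusion.** The point holds in a conditional form. Participants gives one alpha and one power for an unnamed test, while Objectives and Design fix two primary outcomes and two comparators.

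- If either primary at 0.05 counts as success, the false-positive rate is about 8-10% for two outcomes or 10-14% for three scores with one three-arm ANOVA per outcome. It is about 14-25% only with unadjusted pairwise tests.
- If alpha is halved, one-way omnibus power with 135 evaluable is 63%, against 73% at 0.05. If both primaries are required, it is about 61% at score correlation 0.5.

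The error rates assume that all null hypotheses are true, score correlations of 0-0.8 and equal arms. The power figures also read 0.25 as Cohen's f. The 61% further assumes that the two comparators have equal means and that the effect is the same on both outcomes. Clustering by centre is left out, so these figures measure the effect of multiplicity alone and are not the trial's full error rate or power.

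**What to change.** In Objectives and Participants:

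1. Designate one BPI score as the primary pain measure.
2. State one rule that holds the primary false-positive rate at 0.05 over the two outcomes. Two valid choices are 0.025 for that BPI score and 0.025 for the PHQ-9 with unused alpha passed on, or a fixed order of the two. The fixed order keeps the full 0.05 for the first outcome, but the second can be claimed only if the first succeeds.
3. Within each outcome, test either the three-arm difference or the comparators in a stated order, and treat all other p-values as descriptive. As a check, the 0.025 split with ordered comparators (usual care first) and alpha passed on gave 4.6% under the global null at score correlation 0.5.
4. Restate the power in Participants for the named outcome and contrast, at the alpha actually used.

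The cost is about a paragraph of text and, under a split, lower power per primary test: pairwise, with d = 0.53 and 45 per arm, about 59% at 0.025 against 70% at 0.05, before alpha is passed on. No extra enrolment is proposed, so the restated power would be below 80% on the one-way reading, and the protocol should say so.
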